1 PROTOCOL REVISION HISTORY

Date/Name	Description
15Dec2021 [REDACTED]	
Final Protocol, Amendment 1
 
The amendment is being written to change the blood collection tube size from 5 mL for plasma CT-1812 and M6 pharmacokinetic assessment to 6 mL and from 1 mL for whole blood total radioactivity assessment to 2 mL due to commercial availability of the blood collection tubes. Therefore the total blood volume collected in the study will increase from 392 mL to 428 mL. Table 1 in Section 13.4 Blood Volume Drawn for Study Assessments was updated accordingly.
 
In addition, Section 6 Study Events Flow Chart was revised to correct the following discrepancies:
 
• Changed the footnotes of columns EOT/ET and FU to the correct footnotes; i.e., c and d, respectively.• Updated footnote “m” to be consistent with Section 13.3.6 Fecal Sampling and Processing.
02Dec2021 by [REDACTED]	Final Protocol

CONFIDENTIAL

CT1812, CA35306, Final Protocol, Amendment 1_15Dec2021

5 SYNOPSIS

Compound:	CT1812
Clinical Indication:	Alzheimer's Disease (AD) dementia or prodromal mild cognitive impairment (MCI) due to AD
Study Phase and Type:	Phase 1 – absorption, metabolism, excretion, and mass balance study
Study Objectives:	
Primary objectives:
 
• To determine the route(s) of elimination and the overall mass balance of CT1812 following a single oral dose of [¹⁴C]-CT1812 administered in healthy adult male subjects.• To quantitate total radioactivity (TRA) concentration equivalents in whole blood, plasma, urine, and feces following a single oral dose of [¹⁴C]-CT1812 administered in healthy adult male subjects.• To characterize the PK profile of CT1812 and its metabolite, M6, in plasma following a single oral dose of [¹⁴C]-CT1812 administered in healthy adult male subjects.• To characterize the metabolite profile of CT1812 in plasma, urine, and feces following a single oral dose of [¹⁴C]-CT1812 in healthy adult male subjects and identify the chemical identity of each metabolite accounting for more than 10% of circulating TRA. 
Secondary objectives:
 
• [REDACTED]• [REDACTED]• [REDACTED]
Summary of Study Design:	
This is an open-label, single-dose study to assess the absorption, metabolism, excretion, and mass balance for [¹⁴C]-CT1812.
 
Subjects will be admitted to the [REDACTED] on Day -1 and discharged from the [REDACTED] following completion of 168 hours postdose procedures (Day 8).
 
On Day 1, subjects will receive a single oral dose of 300 mg CT1812 (2 capsules) with a microtracer dose of ~1 μCi [¹⁴C]-CT1812 (1 capsule). Whole blood, plasma, urine, and fecal samples will be

CONFIDENTIAL

CT1812, CA35306, Final Protocol, Amendment 1_15Dec2021

	
collected over 168 hours postdose (Day 8) to measure total radioactivity (all samples), CT1812 and M6 metabolite concentrations (plasma), and for metabolite profiling and identification (plasma, urine, and fecal samples).
 
[REDACTED] will attempt to contact all subjects who received the study drug (including subjects who terminate early) using their standard procedures approximately 14 days after dosing to determine if any adverse event (AE) has occurred since the last visit.

Number of Subjects:	Eight (8), healthy, adult male subjects will be enrolled.
Dosage, Dosage Form, Route, and Dose Regimen:	
Study drug will be supplied as capsules of nonradiolabeled CT1812 (powder) and capsules of radiolabeled [¹⁴C]-CT1812 (powder/suspension).
 
The study treatment will consist of 3 capsules: 2 capsules containing CT1812 [REDACTED] and 1 capsule containing ~1 µCi [¹⁴C]-CT1812 ([REDACTED]®).
 
Capsules will be administered orally under fasting conditions on Day 1 at Hour 0 with approximately 240 mL of water. Additional water, up to 50 mL, is permissible to facilitate swallowing multiple capsules.

Key Assessments:	
Mass Balance
 
TRA recovery and the percent of the radioactive dose excreted in the urine and feces will be assessed. Mass balance will be calculated as a sum of the percent of the TRA recovered in urine and feces relative to the administered radioactive dose minus any radioactive dose lost due to emesis (if any occurred).
 
Pharmacokinetics:
 
The following PK assessments will be evaluated, as appropriate:
 
• TRA concentration equivalents are [REDACTED]• TRA concentration equivalents are [REDACTED]

CONFIDENTIAL

CT1812, CA35306, Final Protocol, Amendment 1_15Dec2021

- TRA concentration equivalents [REDACTED]
- CT1218 and M6 concentrations in plasma [REDACTED]
- Ratio of plasma CT1812 to TRA fo [REDACTED].

Metabolite profiling:

CT1812 metabolite profiling will be performed on plasma, urine, and fecal samples. The percent of dose represented by each of the metabolites, if any, will be calculated using the radioactive concentration equivalent data combined with the metabolite profiling data. The percentage of each identified metabolite, if any, to TRA in the plasma will be estimated based on plasma metabolite profiling data. Metabolites accounting for more than 10% of circulating TRA will be identified.

Whole blood to plasma partitioning ratio:

The percentage of TRA in whole blood relative to plasma will be estimated at each time-matched determination of TRA in whole blood and plasma.

Safety:

Safety will be monitored through AEs, 12-lead electrocardiograms (ECGs), vital sign measurements, clinical laboratory tests, physical examinations, ophthalmic examinations, and Columbia-Suicide Severity Rating Scale (C-SSRS). AEs will be tabulated and summary statistics for the 12-lead ECGs, vital signs, and clinical laboratory tests may be computed and provided, as deemed clinically appropriate.

CONFIDENTIAL

CT1812, CA35306, Final Protocol, Amendment 1_15Dec2021

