10 STUDY DESIGN

10.1 Overall Study Design and Plan

This is an open-label, single-dose study to assess the absorption, metabolism, excretion, and mass balance for [¹⁴C]-CT1812.

Eight (8) healthy male subjects will be enrolled.

Screening of subjects will occur within 28 days prior to dosing.

Subjects will be admitted to the [REDACTED] on Day -1 and discharged from the [REDACTED] following completion of 168 hours postdose procedures (Day 8).

On Day 1, subjects will receive a single oral dose of 300 mg CT1812 (2 capsules) with a microtracer dose of ~1 μ Ci [¹⁴C]-CT1812 (1 capsule). Whole blood, plasma, urine, and fecal samples will be collected over 168 hours postdose (Day 8) to measure TRA (all samples), CT1812 and M6 metabolite concentrations (plasma), and for metabolite profiling and identification (plasma, urine, and fecal samples).

Safety will be monitored throughout the study by repeated clinical and laboratory evaluations.

Discontinued subjects may be replaced at the discretion of the Sponsor.

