12 TREATMENTS

12.1 Treatments Administered

Study drug will be supplied as capsules of nonradiolabeled CT1812 (powder) and capsules of radiolabeled [¹⁴C]-CT1812 (powder/suspension).

The study treatment will consist of 3 capsules: 2 capsules containing CT1812 (███████████) and 1 capsule containing ~1 µCi [¹⁴C]-CT1812 (███████████).

Capsules will be administered orally under fasting conditions on Day 1 at Hour 0 with approximately 240 mL of water. Additional water, up to 50 mL, is permissible to facilitate swallowing multiple capsules.

The pharmacy at the █████ will provide the [¹⁴C]-CT1812 dose in individual unit dose containers for each subject.

Subjects will be instructed not to crush, split, or chew the capsules.

The exact clock time of dosing will be recorded.

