13.3.10 Analytical Method

Samples from all subjects will be assayed even if the subjects do not complete the study.

Plasma concentrations of CT1812 and metabolite M6 will be determined using validated analytical methods. Whole blood, plasma, urine, and feces TRA will be determined with liquid scintillation counting or AMS detection. Profiling and identification of metabolites in plasma, urine, and where possible, feces will be conducted using standard laboratory procedures. Specifics of the analytical methods will be provided in separate documents.

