14.3.1.3 Metabolite Profiling

CT1812 metabolite profiling will be performed on plasma, urine, and fecal samples containing sufficient amounts of radioactivity. The percent of dose represented by each of the metabolites, if any, will be calculated using the radioactive concentration equivalent data combined with the metabolite profiling data. The percentage of each identified metabolite, if any, to TRA in the plasma will be estimated based on plasma metabolite profiling data. Metabolites accounting for more than 10% of circulating TRA will be identified.

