6. RUN ACCEPTANCE CRITERIA

For analytical run to be considered acceptable, calibration curve and quality control (QC) samples should meet the acceptance criteria.

For calibration curve, the accuracy of at least 75% of the included non-zero calibration standards must be within 15% of nominal back-calculated concentration and 20% at LLOQ concentration.

For quality control sample acceptance criteria, the accuracy of at least 2/3rd of total QC samples should be within 15%. In addition, the accuracy of at least 50% of QC samples at each concentration level (LQC, MQC and hQC) should be within 15%.

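### Does the plasma CT1812-to-TRA ratio mislead because the drug mass and the radioactivity come from different capsules?

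*Protocol*

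**What the plan says.** Protocol 10.1 gives "a single oral dose of 300 mg CT1812 (2 capsules) with a microtracer dose of" about 1 µCi [14C]-CT1812 in one further capsule. Section 12.1 describes the supplies as "capsules of nonradiolabeled CT1812 (powder) and capsules of radiolabeled [¹⁴C]-CT1812 (powder/suspension"). The contents of both capsule types are partly redacted.

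The two measurements come from different assays. Under 13.3.10, "Plasma concentrations of CT1812 and metabolite M6 will be determined using validated analytical methods", and "Whole blood, plasma, urine, and feces TRA will be determined with liquid scintillation counting or AMS detection". The synopsis (Section 5, Key Assessments) then lists "Ratio of plasma CT1812 to TRA"; the rest of that bullet is redacted.

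Section 14.3.1.3 covers the label-based profile: "CT1812 metabolite profiling will be performed on plasma, urine, and fecal samples containing sufficient amounts of radioactivity", and "The percentage of each identified metabolite, if any, to TRA in the plasma will be estimated based on plasma metabolite profiling data". That sentence names metabolites and not the parent. Section 8.2.2, however, justifies the dose partly by having enough radioactivity to detect parent drug as well as metabolites in plasma.

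The SAP supplied is a bioanalytical plan for CT1812 and M6 and does not mention the ratio. Protocol 14.3 places the detailed summary methods in a statistical analysis plan.

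**The concern.** In a study with one uniformly labelled dose, parent concentration over total radioactivity estimates how much of the circulating radioactivity is unchanged drug. Here the drug mass and the label are swallowed in separate capsules of different description. If the tracer capsule releases or absorbs its contents to a different extent, the ratio moves for a reason unrelated to metabolism. Less tracer absorbed would look like less metabolism, and more tracer absorbed like more.

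Section 8.2.2 makes this easy to overlook because it describes the three capsules as one labelled 300 mg dose. At stake would be a reported parent share that disagrees with the radiochromatographic profile. In an extreme case it would leave no room for the metabolites reported beside it.

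**Working it through.** The documents state no value for this ratio, so there is no figure to reproduce.

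**Inputs from the documents.** Unlabelled dose D = 300 mg and tracer activity A of about 1 µCi (10.1, 12.1); single-dose median half-life 11.1 to 14.0 h (8.1.2); assay run limit 15% (SAP 6).

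**Assumptions.** The relative extent R = F(tracer capsule)/F(unlabelled capsules); the absorption rates used below; linear kinetics; the same first-pass loss for both capsule types; radioactivity converted to mass equivalents at the whole-dose specific activity, 1000 nCi/300 mg = 3.33 nCi/mg.

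**Extent.** Per unit absorbed, let p be the AUC of parent, q the AUC of all drug-related material, and s = p/q the parent's true share.

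- Assay CT1812 AUC = D × F(unlabelled) × p
- TRA AUC in mass equivalents = D × F(tracer) × q
- Listed ratio = s/R
- Profile: 14C-parent/14C-total = [A × F(tracer) × p]/[A × F(tracer) × q] = s, so R cancels

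| True share | R = 0.8 | R = 0.9 | R = 1 | R = 1.25 |
|---|---|---|---|---|
| 20% | 25% | 22% | 20% | 16% |
| 40% | 50% | 44% | 40% | 32% |
| 60% | 75% | 67% | 60% | 48% |
| 80% | 100% | 89% | 80% | 64% |

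**Scale against assay tolerance.** SAP 6 accepts a run when "the accuracy of at least 2/3rd of total QC samples should be within 15" percent. That is a limit, not an expected bias. A bias at the limit would make a true 40% read 0.40 × 0.85 = 34% or 0.40 × 1.15 = 46%, the same as R = 1/0.85 = 1.18 or R = 1/1.15 = 0.87. Moderate departures of R from 1 therefore cannot be told apart from permitted assay error.

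**Rate only, equal extent (R = 1).** I used a one-compartment oral model with unlabelled ka = 2/h, half-lives of 11.1, 12.5 and 14.0 h, and the parent curve standing in for the shape of TRA. The tracer had a lag of 0.25, 0.5 or 1 h, or a slower ka of 0.5/h.

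- AUC0-24 ratio: +0.5% to +3.9%
- AUC0-48 ratio: +0.1% to +0.9%
- Single time points with tracer ka = 0.5/h: factor about 2.9 at 0.5 h, 2.2 at 1 h, 1.5 at 2 h and 1.1 at 4 h, then 0.90 to 0.93 from 12 h on

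A milder difference (ka 2.5/h against 1.25/h) gives 1.53 at 0.5 h, 1.28 at 1 h and 1.07 at 2 h. A rate difference thus barely moves an AUC ratio but can distort early time-point ratios.

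**Which other outputs mix the two sources?**

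- Mass balance (14.3.1.2): radioactivity recovered over radioactivity given. It does not mix them.
- Metabolites above 10% of circulating TRA (14.3.1.3): label over label. It does not mix them.
- Renal clearance (13.3.5): cumulative urinary TRA over an AUC0-inf whose analyte is not stated. With the TRA AUC, R cancels. With the assay CT1812 AUC, the result is multiplied by R. The section is introduced as parameters for urine TRA, so the TRA AUC is the natural reading, but the text does not settle it.

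**The case for a change.** The strongest case for a change is that the algebra is right and the remedy is cheap. The only visible named output relating parent to TRA is the mixed-source one, because 14.3.1.3 names label-based shares for metabolites only. Profiling blood is already drawn at all 18 time points (13.4, Table 1). One line naming the 14C parent peak as the source of the parent's share, and one sentence stating the equal-absorption assumption, would remove the ambiguity.

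Most of that stands as reporting advice; it does not show a fault in the plan. Harm needs two things that the documents do not show: that R differs from 1, and that the ratio is presented as the parent's share. The metric, and any caveat attached to it, lie in redacted text, so neither can be called missing. Section 8.1.2 reports roughly dose-proportional exposure from 10 to 1120 mg and no appreciable food effect at 90 mg. That does not compare these two capsule types, but it gives no sign that extent of absorption is fragile.

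The profile is not a full replacement either. It covers only samples with enough radioactivity, and the protocol does not promise a profile for every subject and time. The assay-based ratio therefore remains useful as supportive information.

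Two cautions survive for whoever writes the report: early time-point ratios should not be read as metabolism, and the analyte in the renal clearance denominator should be stated.

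**Conclusion.** The observation is correct, but no change to the plan follows. The ratio equals the parent's share of circulating radioactivity only if the two capsule types are absorbed to the same extent. Over an assumed R of 0.8 to 1.25 it would read 1.25 to 0.80 times the true share, and at R = 1 there is no shift.

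No visible calculation or decision depends on that reading. Label-based plasma profiling is already a primary objective (Section 9) and yields the parent's share without R wherever the parent peak is measurable. This is a detail that analysts can settle in the statistical analysis plan or the report: take any parent share from the 14C profile and present the assay ratio as supportive, with its assumption stated.

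The conclusion rests on the visible text. It would need another look if the redacted wording made the ratio the definitive measure of the parent's share.

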6 STUDY EVENTS FLOW CHART

Study Procedures ^a	S ^b	Study Days																EOT /ET ^c	FU ^d						
		-1		1								2		3		4		5		6		7			
		Days →	Hours →	C	I	P	0	0.5	1	2	3	4	6	8	12	16 ^f	24	36	48	72	96	120	144	168	
Administrative Procedures																									
Informed Consent		X																							
Inclusion/Exclusion Criteria		X	X																						
Medical History		X																							
Safety Evaluations																									
Full Physical Examination		X																							
Abbreviated Physical Examination			X																						
Symptom-driven Physical Examination ^g																X									
Height		X																							
Weight		X	X																						
C-SSRS Questionnaire		X																				X			
12-Lead ECG		X		X ^h													X					X			
Vital Signs (PR, BP, RR, and T)		X		X ^h													X	X				X			
Hem, Serum Chem ⁱ , and UA		X	X															X					X		
Ophthalmic Examinations		X																					X		
Urine Drug and Alcohol Screen		X	X																						
Cotinine Screen		X																							
HIV/Hepatitis Screen		X																							
AE Monitoring		X															X							X	
ConMed Monitoring		X															X								
Study Drug Administration/ PK																									
[¹⁴ C]-CT1812 Dosing					X																				
Blood for Plasma CT1812 and M6 PK				X ^j		X	X	X	X	X	X	X	X	X	X	X	X	X	X	X	X	X	X		
Blood for Whole Blood TRA				X ^j		X	X	X	X	X	X	X	X	X	X	X	X	X	X	X	X	X	X		
Blood for Plasma TRA				X ^j		X	X	X	X	X	X	X	X	X	X	X	X	X	X	X	X	X	X		
Blood for Plasma Metabolite Profiling and identification				X ^j		X	X	X	X	X	X	X	X	X	X	X	X	X	X	X	X	X	X		
Urine for Metabolite Profiling and TRA ^k				X ^j													X								
Feces for Metabolite Profiling and TRA ^l				X ^m													X								

CONFIDENTIAL

CT1812, CA35306, Final Protocol, Amendment 1 15Dec2021

Study Procedures ^a	S ^b	Study Days																EOT /ET ^c	FU ^d		
		-1		1								2		3	4	5	6	7	8		
		Days →	Hours →	C-I ^e	P	0	0.5	1	2	3	4	6	8	12	16 ^f	24	36	48	72	96	120
Other Procedures																					
Confinement in the CRU															X						
Visit	X																				

- a For details on Procedures, refer to [Section 13](#).
- b Within 28 days prior to dosing.
- c To be performed at discharge from CRU (EOT) or prior to ET from the study.
- d The CRU will attempt to contact all subjects who received the study drug (including subjects who terminate the study early) using their standard procedures approximately 14 days after dosing to determine if any AE has occurred since the last study visit.
- e Subjects will be admitted to the CRU on Day -1, at the time indicated by the CRU. Subjects may be admitted earlier than Day -1 for COVID-19 testing not related to study protocol as per CRU requirements.
- f The 16-hour time point may be on Day 1 or Day 2 depending on the time of dosing on Day 1.
- g Symptom-driven physical examinations may be performed at the PI's or designee's discretion.
- h To be performed within 24 hours prior to dosing.
- i Samples for serum chemistry will be obtained following a fast of at least 8 hours-at the time of screening, however, in case of dropouts or rechecks, subjects may not have fasted for 8 hours prior to when the serum chemistry sample is taken.
- j Predose samples should be stored separately, away from the postdose samples to avoid cross contamination.
- k Urine collection for analysis of TRA and metabolite profiling will be conducted at the following intervals: predose, 0 to 4, 4 to 8, 8 to 12, and 12 to 24 hours postdose, and every 24 hours until Day 8 (168 hours postdose).
- l Fecal collection for the analysis of TRA and metabolite profiling will be conducted predose and in 24-hours intervals for 168 hours postdose.
- m The predose fecal sample is to be obtained within 48 hours prior to dosing. Predose samples should be stored separately, away from the postdose samples to avoid cross contamination.

Abbreviations: AE = Adverse event(s), BP = Blood pressure, C-I = Check-in, C-SSRS = Columbia-Suicide Severity Rating Scale, Chem = Chemistry, ConMeds = Concomitant medication, COVID-19 = Coronavirus Disease-2019, CRU = Clinical research unit, ECG = Electrocardiogram, EOT/ET = End-of-Treatment or early termination, FU = Follow-up, Hem = Hematology, HIV = Human immunodeficiency virus, P = Predose, PI = Principal Investigator, PK = Pharmacokinetics, PR = Pulse rate, RR = Respiratory rate, S = Screening, T = Temperature, TRA = Total radioactivity, UA = Urinalysis.

7 ABBREVIATIONS

Pharmacokinetic parameter abbreviations and definitions may be found in [Sections 13.3.2](#), [13.3.5](#), and [13.3.7](#)

µCi	Microcurie
Abeta	Beta amyloid
AD	Alzheimer's Disease
AE	Adverse event
AMS	Accelerator mass spectrometry
BMI	Body mass index
C-SSRS	Columbia-Suicide Severity Rating Scale
CFR	Code of Federal Regulations
CKD-EPI	Chronic Kidney Disease Epidemiology Collaboration
CNS	Central nervous system
COVID-19	Coronavirus Disease-2019
CRF	Case report form
██████████	██████████
CSF	Cerebrospinal fluid
%CV	Coefficient of variation
CYP	Cytochrome P450
ECG	Electrocardiogram
EDTRS	Early Treatment Diabetic Retinopathy Study
F	Absolute bioavailability
FDA	Food and Drug Administration
GCP	Good Clinical Practice
GI	Gastrointestinal
HBsAg	Hepatitis B surface antigen
HCV	Hepatitis C virus
HIV	Human immunodeficiency virus
HPBCD	Hydroxypropyl-β-cyclodextrin
IB	Investigator's Brochure
ICF	Informed Consent Form

CONFIDENTIAL

CT1812, CA35306, Final Protocol, Amendment 1_15Dec2021

ICH	International Council for Harmonisation
IND	Investigational New Drug
IRB	Institutional Review Board
IV	Intravenous
KRBC/PL	Ration of partitioning between red blood cells and plasma
LLOQ	Lower level of quantitation
MAD	Multiple ascending dose
MCI	Mild cognitive impairment
n	Sample size
No.	Number
P-gp	P-glycoprotein
PI	Principal Investigator
PK	Pharmacokinetic(s)
PO	Per os; oral
QA	Quality Assurance
QD	Once daily
QTcF	Corrected value of the interval between the Q and T waves on the electrocardiogram tracing, corrected QT interval by Fredericia.
SAD	Single ascending dose
SAE	Serious adverse event
SAP	Statistical analysis plan
SEDDS	Self-emulsifying drug delivery system
TEAE	Treatment-emergent adverse events
TRA	Total radioactivity
US	United States
USA	United States of America

8 INTRODUCTION

8.1 Background

CT1812 is an oral formulation in current development for the treatment of Alzheimer's Disease (AD) dementia and Mild cognitive impairment (MCI) due to AD. Cognition Therapeutics, Inc., has discovered that oligomeric forms of the beta amyloid 1-42 (Abeta) protein binds specifically and reversibly to a single, saturable receptor site on neuronal synapses (Izzo 2014a; Cahill et al, 2016) and that brain penetrant small molecules that act as antagonists at the sigma-2 receptor can both prevent oligomer binding in vitro and displace bound oligomers from these receptor sites and stop synapse loss in vitro. Currently, there are no approved products for the treatment of MCI or established AD that function by blocking the binding and pathological activity of soluble Abeta oligomers. CT1812 is a brain penetrant drug designed to selectively target and displace the oligomeric form of Abeta (Abeta oligomers) bound to neuronal receptors at synapses by a new and differentiated mechanism of action. CT1812 not only prevents and displaces binding of amyloid-beta oligomers to neuronal synapses, but was shown to prevent and restore Abeta oligomer-induced synapse loss and reverses downstream alterations in neuronal trafficking in cultured rat neurons.

